### **6.1.2.2. Reactogenicity Data**

#### **6.1.2.2.1. Local Reactions**

- Endpoints: Participants reporting local reactions (redness, swelling, and pain at the injection site) and severity of the reactions ([Section 3.5.2.1](#)).
- Analysis time points: 7-Day period following each vaccination.
- Analysis population: Safety population ([Section 4](#)).
- Reporting summaries:
  - Maximum severity for local reactions  
The number of participants reporting e-diary data transmitted for at least 1 day (these values are used as the denominators for the percentage calculations), the number of participants reporting at least 1 occurrence of the specified reaction or any reaction by the maximum severity grade, the observed proportion of participants, and their exact 2-sided CIs (Clopper and Pearson).
  - Duration of each local reaction  
Number of participants reporting the specified reaction, mean, median, range (minimum, maximum), standard deviation, and number of unknown durations.
  - Onset of local reactions  
The number of participants reporting the specified reaction or any reaction, mean, range (minimum, maximum), and standard deviation.
  - Figures  
A bar graph showing the percent incidence for the specified reaction and for any reaction, by day.

#### **6.1.2.2.2. Systemic Events**

- Endpoints: Participants reporting systemic events (fever, decreased appetite, drowsiness, and irritability for participants 1 to  $\leq 2$  years of age; and fever, fatigue, headache, vomiting, diarrhea, muscle pain, and joint pain for participants  $>2$  years of age) and severity of the events ([Section 3.5.2.2](#)).

- Analysis time points: 7-Day period following each vaccination.
- Analysis population: Safety population ([Section 4](#)).
- Reporting summaries:

- Maximum severity for systemic events

The number of participants reporting e-diary data transmitted for at least 1 day (these values are used as the denominators for the percentage calculations), the number of participants reporting at least 1 occurrence of the specified event or any event by the maximum severity grade, the observed proportion of participants, and their exact 2-sided CIs (Clopper and Pearson).

- Duration of each systemic event

Number of participants reporting the specified event, mean, median, range (minimum, maximum), standard deviation, and number of unknown durations.

- Onset of systemic events

The number of participants reporting the specified event or any event, mean, range (minimum, maximum), and standard deviation.

- Figures

A bar graph showing the percent incidence for the specified event and for any event, by day.

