### 3.4.2. E-Diary Transmission

An e-diary will be considered transmitted if any data for the local reactions, systemic events, or use of antipyretic/pain medication are present for any day. If all data are missing for all items on the e-diary for all 7 days after vaccination, then the e-diary will be considered not transmitted. An e-diary will be considered completed if all expected data for all 7 days are available (ie, not missing). Otherwise, the e-diary will be considered incomplete. For any given day, an e-diary will be considered complete if all expected data are available.

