**Table 6. Derived Variables for Each Local Reaction**

Variablea	Yes (1)	No (0)	Missing (.)
Any day (Day 1-7)	Participant reports the reaction as “yes” on any day from Day 1 through Day 7.	Participant reports the reaction as “no” on all 7 days or as a combination of “no” and missing on all 7 days.	Participant’s response to the reaction is missing on all 7 days.

- a. The variable will be defined for each of the 3 local reactions.

For “any local reaction” on any day, a similar definition can be applied as given in Table 7 below.

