**Table 10. Ranges for Fever**

	Mild Grade 1	Moderate Grade 2	Severe Grade 3	Grade 4
Fever	$\geq 37.5^{\circ}\text{C}; \leq 38.4^{\circ}\text{C}$	$\geq 38.5^{\circ}\text{C}; \leq 38.9^{\circ}\text{C}$	$\geq 39.0^{\circ}\text{C}; \leq 40.0^{\circ}\text{C}$	$>40.0^{\circ}\text{C}$

The presence or absence of each systemic event on a given day is defined as follows:

- = “Missing,” if the value is missing on a given day;
- = “Yes,” if the participant reports a temperature  $\geq 37.5^{\circ}\text{C}$  for fever **or** “mild,” “moderate,” “severe,” or “Grade 4” for the remaining events on a given day;
- = “No,” if the participant reports a temperature  $<37.5^{\circ}\text{C}$  for fever **or** “none” for the remaining events on a given day.

For each systemic event, the following variables will be derived:

1. Presence or absence of each systemic event on each day (Days 1-7) after each vaccination.
2. Presence or absence of each systemic event on “any day (Day 1-7)” after each vaccination.
3. Maximum severity of each systemic event on “any day (Day 1-7)” after each vaccination.
4. Maximum severity of each systemic event on “any day (Day 1-7)” after any vaccination.
5. Presence or absence of any systemic event on each day (Days 1-7) after each vaccination.
6. Presence or absence of any systemic event on “any day (Day 1-7)” after each vaccination.
7. Duration of each systemic event after each vaccination.
8. Onset day of each systemic event after each vaccination.
9. Onset day of any systemic event after each vaccination.

The derivation of these variables is similar to the derivation of the variables for local reactions (Section 3.5.2.1). “Any systemic event” includes any fever, decreased appetite, drowsiness, or irritability for participants 1 to  $\leq 2$  years of age; and any fever, fatigue, headache, vomiting, diarrhea, muscle pain, or joint pain for participants  $>2$  years of age.

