Major protocol violations will be determined by clinical review (through the data handling memo). A major protocol violation is a protocol violation that, in the opinion of the sponsor's study medical monitor, would materially affect assessment of safety and/or immunogenicity, eg, participant receipt of a prohibited vaccine or medication that might affect immune response or a medication error with suspected decrease in potency of the vaccine. The sponsor's medical monitor will identify those participants with protocol violations before any immunogenicity analysis is carried out.

For local reactions, systemic events, fever, and use of antipyretic and/or pain medication, the definition of the denominators for the percentage calculations are described in [Section 3.5.2](#) based on e-diary record. In addition, these tables will be generated without e-diary data that have been confirmed by the participant to have been entered in error. Data-entry errors will be discussed in the clinical study report text and documented in a separate listing.

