### 5.2. General Methods

Descriptive summary statistics will be provided for all endpoints. Unless otherwise explicitly stated, descriptive statistics for continuous variables are n, mean, median, standard deviation, minimum, and maximum. Descriptive statistics for categorical variables are the proportion (%) and the n (the numerator) and N (the denominator) used in the calculation of the proportion.

All of the safety, tolerability, and immunogenicity data will be summarized by age group.

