### **5.3.3. Reactogenicity Data**

For derived variables based on reactogenicity data, if any day of the 7-day e-diary is available, the “any day (Day 1-7)” data will be considered nonmissing.

The reactogenicity data are collected through the e-diary, which does not allow participants to skip the question. Therefore, for a specific day, as long as the e-diary data are transmitted for that day, all of the reactogenicity data for the participant on that day are nonmissing. No missing reactogenicity data will be imputed other than what is described in [Section 3.5.2](#).

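### The denominator in SAP 6.1.2.2.2 is not limited to participants asked about the event, so a pooled paediatric table could dilute the nine age-specific systemic events

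*SAP*

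**What the plan says.** - **Denominator.** SAP 6.1.2.2.2 applies one rule to each specified systemic event and to any event: "The number of participants reporting e-diary data transmitted for at least 1 day (these values are used as the denominators for the percentage calculations"). SAP 6.1.2.2.1 uses the same wording for local reactions.
- **Transmission.** SAP 3.4.2 defines it for the diary as a whole: "An e-diary will be considered transmitted if any data for the local reactions, systemic events, or use of antipyretic/pain medication are present" for any day.
- **Items by age.** In SAP 3.5.2.2, fever is collected from everyone. Decreased appetite, drowsiness and irritability are collected only at 1 to ≤2 years. Fatigue, headache, vomiting, diarrhoea, muscle pain and joint pain are collected only above 2 years.
- **Reporting level.** SAP 5.2: "All of the safety, tolerability, and immunogenicity data will be summarized by age group". The groups named in SAP 5.1 are adults (16 and older) and children (1 to <16), so both paediatric item lists fall in one group.
- **Cross-reference.** SAP 4 says of these tables that "the definition of the denominators for the percentage calculations are described in" Section 3.5.2.
- **What Section 3.5.2 contains.** It gives no denominator. Table 6 sets a local-reaction variable to missing when the participant's "response to the reaction is missing on all 7 days". For systemic events, "The derivation of these variables is similar to the derivation of the variables for local reactions". One derived variable spans all doses: "Maximum severity of each systemic event on “any day (Day 1-7)” after any vaccination".

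**The concern.** The denominator wording does no harm for local reactions, because all three are asked at every age. Carried over unchanged to systemic events, it meets items that part of the paediatric group never sees. Nothing in the denominator sentence restricts the count to children who were asked.

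The percentage of participants with systemic events after each vaccination is a primary safety estimand for the 0.25 mL group (SAP Table 2). Read literally, the rule makes every age-specific event look rarer than it was among the children who could report it, and it makes the exact confidence interval too narrow. The pooled paediatric table would also disagree with the SAP 6.4 age subsets for the same children. Two programmers, one working from SAP 6.1.2.2.2 and the other from the missing class in Section 3.5.2, could produce different percentages from the same data.

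**Working it through.** The plan gives no reactogenicity rate or numeric denominator, so there is no figure of its own to reproduce. The check has three steps.

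**1. Where the two rules agree and where they part**

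| Case | SAP 6.1.2.2.2, literal | Missing class in SAP 3.5.2 |
|---|---|---|
| Item asked, at least 1 day transmitted | counted | counted (any-day variable nonmissing, SAP 5.3.3) |
| Item asked, no day transmitted | not counted | missing, not counted |
| Item not asked at that age, at least 1 day transmitted | **counted** | missing, not counted |

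The rules differ only in the last row.

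**2. Which results fall in that row**

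- Ten systemic items are listed: 1 common (fever), 3 for the youngest children and 6 for those above 2 years. So 3 + 6 = 9 are age-specific.
- All adults share one item list. Fever and the three local reactions are asked at every age.
- The any-systemic-event variable is defined on each child's own list, so every transmitted diary belongs in its denominator.
- The primary hypothesis tests concern seropositivity and do not use these data.
- The SAP 6.4 subsets are 1 to ≤2, 3 to ≤6 and 7 to ≤15 years. With age in completed years (SAP 3.4.1), the first cut matches the item split, so there is no dilution within a subset.

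Only the nine age-specific items in a pooled 1 to <16 table are affected.

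**3. Size**

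Input from the documents: 65 children planned (Protocol 9.2). Assumptions, because the documents do not give them: all 65 transmit a diary; k of them are aged 1 to ≤2, with k from 5 to 26; the rate among those asked is 40% for a youngest-age item and 33.3% for an older-age item.

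Shown rate = rate among those asked × (number asked ÷ number of diaries).

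| k | Factor, youngest-age items (k/65) | Factor, older-age items ((65 − k)/65) |
|---|---|---|
| 5 | 5/65 = 0.077 | 60/65 = 0.923 |
| 20 | 20/65 = 0.308 | 45/65 = 0.692 |
| 26 | 26/65 = 0.400 | 39/65 = 0.600 |

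Clopper-Pearson 95% limits for x out of n: the lower limit is the 0.025 quantile of Beta(x, n − x + 1) and the upper limit is the 0.975 quantile of Beta(x + 1, n − x).

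| k | Item | Among those asked | Shown over all diaries |
|---|---|---|---|
| 5 | irritability | 2/5 = 40.0% (5.3 to 85.3) | 2/65 = 3.1% (0.4 to 10.7) |
| 5 | fatigue | 20/60 = 33.3% (21.7 to 46.7) | 20/65 = 30.8% (19.9 to 43.4) |
| 20 | irritability | 8/20 = 40.0% (19.1 to 63.9) | 8/65 = 12.3% (5.5 to 22.8) |
| 20 | fatigue | 15/45 = 33.3% (20.0 to 49.0) | 15/65 = 23.1% (13.5 to 35.2) |

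For irritability with k = 20, the interval shrinks from 63.9 − 19.1 = 44.8 points to 22.8 − 5.5 = 17.3 points. Its upper limit of 22.8% lies below the 40.0% observed among the children asked.

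**The case against.** **A reader might infer that SAP 6.1.2.2.2 contradicts SAP 4.** The documents do not support that. SAP 4 offers no rival denominator, only a reference to Section 3.5.2, and that section states none. The tension comes from the missing class in Table 6, a local-reaction table extended to systemic events by analogy. For every item a child is asked, the two rules give the same count.

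**A reader might also infer that SAP 5.3.3 orders unasked items to be counted as non-events,** because on a transmitted day "all of the reactogenicity data for the participant on that day are nonmissing". That sentence rests on the premise that the diary does not let a question be skipped, so it is naturally read as covering questions actually presented. SAP 3.5.2.2 assigns a negative answer only when the participant reports none, or a temperature below 37.5°C.

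**A within-stratum reading is open.** The endpoint bullet of SAP 6.1.2.2.2 itself ties each item to its age range, as do Table 2 and Section 3.5.2.2. On that basis fatigue is not an endpoint for a one-year-old, and a careful programmer might restrict the count unprompted. This stands as a plausible reading. But the denominator clause in the same section carries no such limit, and it is the only explicit denominator the SAP gives for these events.

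**The harm is limited.** No table shell is given, so the pooled layout is inferred from SAP 5.2. The SAP 6.4 subsets already plan undiluted rates, and the diary count used as denominator is itself reported, so a pooled N would be visible. All of this stands. It bounds the problem but does not correct the main paediatric table.

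**Conclusion.** The point holds in limited form. The one explicit denominator for systemic events is not restricted to participants asked about the event, and the reference in SAP 4 does not supply the restriction. This is a missing qualifier and an incomplete cross-reference, in a rule that produces diluted percentages if applied as written.

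If children are pooled and the rule is taken literally, rates are multiplied by 0.08 to 0.40 for the three youngest-age items and by 0.92 to 0.60 for the six older-age items, for 5 to 26 of 65 children aged 1 to ≤2. That age mix, the event rates and complete diary transmission are assumptions. The starkest contrast (40.0% against 3.1%) belongs to the low end of the range. If items are reported within their age stratum, or unasked items are treated as missing, there is no dilution. The correction should be made because these are primary safety results and the error can only run towards fewer events.

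**What to change.** In SAP 6.1.2.2.2:

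- For each specified event and dose, define the denominator as participants whose age-specific diary at that dose contained the event and who transmitted at least one day after that dose. Alternatively, report age-specific items only within their age stratum.
- Apply the same restriction to the maximum-severity summary across all vaccinations: participants asked about the event, with at least one transmitted day after at least one dose at which it was asked.
- Show a per-event N in the paediatric table.
- Keep all transmitted diaries as the denominator for fever and for any systemic event.

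In SAP 4, replace the reference to Section 3.5.2 with one to this rule, or state the rule in Section 3.5.2.

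The cost is a few sentences of SAP text and an extra N per row. No new data are needed. Intervals for the age-specific events become wider because fewer children are counted, and that width reflects the information actually collected.

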## 6.2. Secondary Endpoints

### 6.2.1. Seropositivity Based on TBEV-Neutralizing Antibody Levels (Achieving NT Titer $\geq 1:10$ ) 4 Weeks After the Second Dose

#### 6.2.1.1. Main Analysis

- Estimand strategy: Hypothetical.
- Analysis set: Evaluable immunogenicity population for the second dose ([Section 4](#)).
- Analysis methodology: Descriptive summary statistics.
- Intercurrent events and missing data: For participants who discontinue, all collected data will be included; intermediate missing values will not be imputed.
- Reporting results: n (the number of seropositive participants), N (the size of the analysis population), point estimate (seropositivity rate), and the exact 2-sided 95% CI will be calculated using the Clopper-Pearson method for the seropositivity rate based on the immune response determined by NT 4 weeks after the second vaccination. NT titers  $\geq 1:10$  are considered seropositive.

CCI

## 6.2.2. TBEV-Specific Neutralizing Antibody Titer 4 Weeks After the Second and 4 Weeks After the Third Dose

### 6.2.2.1. Main Analysis

- Estimand strategy: Hypothetical.
- Analysis set: Evaluable immunogenicity population ([Section 4](#)). GMT, LLOQ, and RCDC analysis after the second vaccination and GMFR from baseline to 4 weeks after the second vaccination will be conducted based on the evaluable immunogenicity population for the second dose as well.
- Analysis methodology: Descriptive summary statistics.
- Intercurrent events and missing data: For participants who discontinue, all collected data will be included; intermediate missing values will not be imputed.
- Reporting summaries:
  - GMTs of neutralizing antibody at each available time point will be descriptively summarized for each age group, along with associated 2-sided 95% CIs.
  - GMFRs and associated 2-sided 95% CIs will be provided for neutralizing antibody titer from baseline to 4 weeks after the second vaccination and 4 weeks after the third vaccination, and from 4 weeks after the second vaccination to 4 weeks after the third vaccination.
  - Numbers and proportions of participants with neutralizing antibody titer  $\geq$ LLOQ at each available time point and associated exact 2-sided CIs based upon the observed proportion of participants will be summarized.
  - Empirical RCDCs for TBEV-neutralizing antibody titers will be generated by each combination of available time points and age groups.

CCI

CCI

## 6.4. Subset Analyses

Subset analyses for all of the safety endpoints will be conducted based on the subset defined by age in the pediatric group. Three categories of age will be considered: 1 to  $\leq 2$  years of age, 3 to  $\leq 6$  years of age, and 7 to  $\leq 15$  years of age.

Subset analyses for the following endpoints will be conducted based on the subgroup by baseline CCI [REDACTED]

[REDACTED] All subset analyses will be performed by age group, and the analysis population will be the evaluable immunogenicity population and/or the evaluable immunogenicity population for the second dose as well, if appropriate. If there is no CCI [REDACTED] case at baseline, these subset analyses will not be conducted.

- Primary endpoint
  - Seropositivity based on TBEV-neutralizing antibody levels (achieving NT titer  $\geq 1:10$ ) 4 weeks after the third dose.
- Secondary endpoints
  - Seropositivity based on TBEV-neutralizing antibody levels (achieving NT titer  $\geq 1:10$ ) 4 weeks after the second dose.
  - TBEV-neutralizing antibody titer 4 weeks after the second and 4 weeks after the third dose.

Additional subset analysis (not defined here) may also be performed if deemed necessary.

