#### **Participants >2 to $<$ 12 Years of Age**

**Table 4. Grading Scale for Local Reactions for Participants >2 to  $<$ 12 Years of Age**

	Mild Grade 1	Moderate Grade 2	Severe Grade 3a	Grade 4b
Redness	>0 cm to 2.0 cm (1 to 4 measuring device units)	>2.0 cm to 7.0 cm (5 to 14 measuring device units)	>7.0 cm (>14 measuring device units)	Necrosis or exfoliative dermatitis b

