**Participants ≥12 Years of Age****Table 5. Grading Scale for Local Reactions for Participants ≥12 Years of Age**

	Mild Grade 1	Moderate Grade 2	Severe Grade 3a	Grade 4b
Redness	>2.0 cm to 5.0 cm (5 to 10 measuring device units)	>5.0 cm to 10.0 cm (11 to 20 measuring device units)	>10 cm (>20 measuring device units)	Necrosis or exfoliative dermatitis b
Swelling	>2.0 cm to 5.0 cm (5 to 10 measuring device units)	>5.0 cm to 10.0 cm (11 to 20 measuring device units)	>10 cm (>20 measuring device units)	Necrosis b
Pain at the injection site	Does not interfere with activity	Interferes with activity	Prevents daily activity	Emergency room visit or hospitalization for severe pain at the injection site

- a. Participants experiencing local reactions >20 caliper units (>10 cm) are to be seen by or contact the study site; an unscheduled visit may be required.
- b. Grade 4 assessment must be made by an investigator; Grade 4 will not be collected in the e-diary but will be collected in the case report form. The severity of the local reaction should be graded using the AE severity grading scale provided in the protocol.

For each local reaction, the derivation of whether or not the specific reaction occurred on “any day (Day 1-7)” will be made. The derivation of this variable is given in Table 6 below.

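### Paediatric redness and swelling rates mix two size thresholds in the pooled and 7 to ≤15 rows; common cut-offs and a footnote would make them readable

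*SAP*

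**What the plan says.** Redness and swelling are recorded in device units of 0.5 cm and graded at analysis. SAP 3.5.2.1 counts either reaction as present only from the smallest diameter in the table for the child's age.

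- Under 12 (SAP Tables 3 and 4, same unit ranges): mild is ">0 cm to 2.0 cm (1 to 4 measuring device units", moderate is ">2.0 cm to 7.0 cm (5 to 14 measuring device units" and severe is ">7.0 cm (>14 measuring device units".
- From 12 (SAP Table 5): mild is ">2.0 cm to 5.0 cm (5 to 10 measuring device units", moderate is ">5.0 cm to 10.0 cm (11 to 20 measuring device units" and severe is more than 20 units.

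The protocol's local-reaction tables (8.2.2.1) use the same unit ranges.

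SAP 5.2 summarises all safety data by age group, so children from 1 to under 16 form one row. SAP 6.4 then adds: "Subset analyses for all of the safety endpoints will be conducted based on the subset defined by age in the pediatric group". It continues: "Three categories of age will be considered", and lists 1 to ≤2, 3 to ≤6 and 7 to ≤15 years. Beyond these it says only: "Additional subset analysis (not defined here) may also be performed if deemed necessary". SAP 6.1.2.2.1 reports each reaction by maximum severity grade, with exact confidence intervals.

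**The concern.** The grading changes at age 12, but no planned paediatric row is cut there. Two rows therefore add together children counted from 1 unit and children counted from 5 units: the pooled paediatric row and the 7 to ≤15 row. Even if true diameters were the same at every age, these rates would move with the age mix. The 7 to ≤15 row could also look less reactogenic than the 3 to ≤6 row through definition alone.

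The planned grade rows cannot undo this, because mild in a mixed row combines 1–4 units (under 12) with 5–10 units (12 and over).

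What is at stake is how a set of primary safety percentages can be read. They are descriptive, no comparison between ages is tested, and the seropositivity criterion is untouched.

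**Working it through.** The documents state no reaction rate, so there is no figure of the plan's own to reproduce.

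**Step 1: apply both scales to the same peak diameter.**

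| Peak (units) | Under 12 (Tables 3, 4) | 12 and over (Table 5) |
|---|---|---|
| 1–4 | mild | not counted |
| 5–10 | moderate | mild |
| 11–14 | moderate | moderate |
| 15–20 | severe | moderate |
| over 20 | severe | severe |

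The 1 to ≤2 and 3 to ≤6 rows each use one threshold, and in them moderate plus severe already equals ≥5 units. Only the pooled and 7 to ≤15 rows are mixed.

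**Step 2: write the mixed rate.** Let s be the share of children peaking at 1–4 units, b the share peaking at ≥5 units, and w the share of the row aged 12 or over. To isolate the definition, take s and b as equal at all ages. Then:

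- mixed rate = (1 − w)(s + b) + w·b = s + b − s·w
- against a 1-unit rule for all (s + b), it is lower by s·w
- against a 5-unit rule for all (b), it is higher by s·(1 − w)

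Example with s = 15% and b = 5%: the rate is 20.0% at w = 0, 16.25% at w = 25% and 12.5% at w = 50%. The last value is 7.5 points below the 1-unit rate of 20% and 7.5 points above the 5-unit rate of 5%.

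**Step 3: put in a range.** Neither s nor w is in the documents. Assume even single years of age, so w = 4/9 in 7 to ≤15 (ages 12–15 out of 7–15) and w = 4/15 pooled (out of 1–15). Differences are in percentage points.

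| s | 7 to ≤15: below 1-unit rule | 7 to ≤15: above 5-unit rule | Pooled: below 1-unit rule | Pooled: above 5-unit rule |
|---|---|---|---|---|
| 2% | 0.9 | 1.1 | 0.5 | 1.5 |
| 5% | 2.2 | 2.8 | 1.3 | 3.7 |
| 10% | 4.4 | 5.6 | 2.7 | 7.3 |
| 20% | 8.9 | 11.1 | 5.3 | 14.7 |
| 30% | 13.3 | 16.7 | 8.0 | 22.0 |

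Against the 1-unit rule, the number of children not counted among the planned 65 is 65 × 4/15 × s, from 0.3 (s = 2%) to 5.2 (s = 30%). If w in 7 to ≤15 runs from 20% to 60%, the shortfall runs from 0.20 × 2% = 0.4 points to 0.60 × 30% = 18.0 points.

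The combined row for any local reaction is affected only where a small reaction occurs without another counted reaction, such as pain. That cannot be quantified here.

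**Step 4: look for a remedy in the plan.** No visible text sets a cut at 12 or a common diameter. SAP sections 3.3 and 6.3 and one row of the protocol's safety analysis table (9.4.2) are not visible, so this holds for the visible text only.

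**The case against.** The strongest reply is that the plan does what it says. Protocol 8.2.2 describes the grading as deliberately adapted from adult and adolescent guidance, and presence is openly defined by age-specific tables. A pooled percentage then has a clear meaning: children with a reaction on the scale for their age. The rates are descriptive, further subsets are allowed, and demographic listings would let a reader recover the age mix. At small s the pooled effect is a fraction of a child to about two children, well inside the sampling error: an observed 26/65 has a 95% CI of 28.0% to 52.9%.

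Most of this stands. The scales should stay, and nothing here is a contradiction. But an optional, undefined subset commits the sponsor to nothing. An age listing also does not give the reader a rate at a common diameter.

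A reader might infer two stronger things:

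- **That the plan understates paediatric reactogenicity.** The documents do not support this. The mixed rate is low against a 1-unit rule and high against a 5-unit rule, and neither is established as the reference.
- **That children who turn 12 during the study switch tables, so that rates drift downward by dose 3.** The SAP never states such a switch. The only age it defines is age at Day 1 (SAP 3.4.1). The rule that selects the table should be named, but no effect should be attributed to it.

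**Conclusion.** The point holds as an inexpensive improvement to descriptive safety reporting. The pooled paediatric and 7 to ≤15 rates for redness and swelling mix a 1-unit and a 5-unit definition, and the planned grade rows cannot separate them. That the rates depend on the share aged 12–15 follows from the tables, and disappears only if no child peaks at 1–4 units.

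The size is unknown. The tabulated ranges rest on three assumptions: even ages, diameters distributed alike at all ages, and s between 2% and 30%. No hypothesis test, sample size or decision rule is affected.

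**What to change.** Keep the age-specific grading.

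1. In SAP 6.1.2.2.1, add the number and percentage of children with redness, and with swelling, at ≥5 units and at >14 units after each dose. Show these for all children and for each SAP 6.4 subset. The ≥5 cut is the lowest grade from age 12. The >14 cut is the severe limit under 12 and the highest cut-off recorded at every paediatric age, because the diary range under 12 ends there (protocol 8.2.2.1).
2. Footnote the pooled paediatric and 7 to ≤15 rows to say that two sets of thresholds apply.
3. As a clarification only, name in SAP 3.5.2.1 the age that selects the grading table: age at Day 1 or another stated age.

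The cost is SAP wording, a footnote and a few descriptive rows (2 reactions × 2 cut-offs = 4 per dose in each group). No new data are needed, since units are recorded and graded at analysis. The drawback is wide intervals in the subsets: with even ages the 3 to ≤6 row would hold about 65 × 4/15 = 17 children, and an observed 4/17 has a 95% CI of 6.8% to 49.9%.
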